We propose to obtain consent from 300 adult smokers interested in quitting smoking. Of those who give consent we expect to identify 80 participants who meet all inclusion and exclusion criteria with the aim of identifying 68 participants who provide useable data. During a phone screening interview, the study will be described in detail and preliminary participant characteristics (e.g. age, number of cigarettes per day) will be assessed. Those participants who meet criteria for participation will be invited to our offices for an informed consent and screening visit. Potential participants will be instructed to bring a valid government issued photo ID to the screening session to confirm age and identity. Identifying

information from the phone screen for the participants who do not meet inclusion criteria will be kept until recruitment for this study is completed.

Screening Session: During the screening session all aspects of the study will be described to subjects and informed consent will be obtained. A standardized PowerPoint presentation will be used to discuss the procedures, risks and benefits with the participant as well as their rights as a research participant. If consent is given we will collect breath and saliva samples in order to verify smoking status and blood alcohol level (BAL). Questionnaires on smoking history, family smoking history, nicotine dependence, and mood will be collected. Participants will also be asked about medical history and complete the Brief Medical History Questionnaire and the Patient Health Questionnaire. Indicating certain items, such as suicidal ideation, significant depression, significant anxiety, or eating disorder, on the Patient Health Questionnaire will trigger medical review by the study physician and emergency referral to psychiatric services if necessary. Research staff will refer to the PrimeMD Evaluation Form when reviewing responses on the Patient Health Questionnaire. Physiological measures such as heart rate, blood pressure, weight, and height will also be measured to assess general health.

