Participants will complete a baseline assessment of cue-reactivity. Participants will view blocks of smoking and non-smoking environment and proximal cues and will complete craving assessments. During the task, heart rate and respiration will be measured using a BIOPAC system. Mood and withdrawal will be assessed at the end of the task.

Participants will be introduced to the digital camera that they will use to capture images of their personal environments and will be given specific guidelines to follow while taking pictures. All information regarding the recording of events, picture taking, and camera operation (e.g. recharging, storage) will be reviewed. Any questions from participants regarding the use of the camera will be discussed. Participants will also be allowed to take pictures with their own personal devices and email them to study staff. If participants choose to take pictures with a device other than the lab camera provided, the camera on the device must have a photo resolution of at least 72 dpi. All participants will be given 2 disposable lighters with stickers attached reminding them to take pictures of smoking locations. Participants will be asked to take the pictures over the course of 1-2 weeks in order to obtain enough useable photographs before returning to the lab for the camera return session.

Camera Return Session/Randomization: Once participants have collected photographs of personal smoking environments they will return to the lab with the camera 1-2 weeks after the training session. The information from the camera will be uploaded, examined, and reviewed with the participant to ensure enough useable pictures were taken. If the images are acceptable for use then they will continue with the visit. If the pictures do not follow the guidelines for acceptable photographs or if there are not enough pictures the RA will review the guidelines for acceptable pictures with the participant and schedule the camera return session for the following week.

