MCE Sessions: Participants will be asked to smoke the assigned cigarettes for the next three weeks. During those three weeks they will come into the lab for 2 visits per week (at least 48 hours apart) to undergo MCE and complete questionnaires. Participants will be instructed to return their remaining product, empty cigarette packs, and used patches at each visit. Additional VLNC cigarettes and nicotine patches will be provided as needed at each visit. Smoking behavior and patch use will be assessed by self-report using the Timeline Follow-Back procedure at each visit. CO, BAL, vitals, and weight will be measured at the beginning of each MCE session. Following physiological measures, participants will be seated in front of a computer monitor. Participants will be video recorded during the session to gather data about their smoking behavior. Heart rate and respiration will be measured using a BIOPAC system at the first and last MCE sessions. Participants will complete baseline craving and mood surveys. Participants will view picture stimuli depicting smoking environments including their personal smoking environments (MCE+ condition) or nature environments (MCE- condition) and will be instructed to imagine they are in the location depicted in each image. There will be a total of 10 blocks of images and participants will indicate their current craving level during the task. Each image will be shown for 15 seconds. After block 5, participants will have a 5 minute break and then resume the task. Participants will be instructed to light and smoke a VLNC cigarette at the beginning of the task and following block 2, the 5 minute break, and block 7 (4 cigarettes total). At the end of the session, CO, vitals, and withdrawal and mood will be assessed.

At the end of the three week treatment period, participants will quit smoking while continuing to wear the nicotine patch.

Post-Quit Test Session: Participants will return to the lab following 24 hour abstinence for a post-quit test session where cue-reactivity and withdrawal will be assessed as done during baseline. Abstinence will be verified by expired breath CO level \leq 6 ppm. If the participant does not meet abstinence criteria, s/he will only receive compensation for completing the visit, not for maintaining abstinence.

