Abstinence Period Visits: During a 10 week abstinence period, participants will be followed and will be provided with nicotine patches. Participants will return to the lab 1 week, 3 weeks, 6 weeks, and 10 weeks following the quit day. Participants wearing a 21 mg/d patch prior to quitting will step-down to a 14 mg/d patch at 6 weeks post-quit and step-down again to a 7 mg/d patch at 8 weeks post-quit. Participants wearing a 14 mg/d patch prior to quitting will step-down to a 7 mg/d patch at 6 weeks post-quit and continue this treatment for the duration of the study. Physiological measures will be collected and participants will complete questionnaires at each visit. Smoking behavior will be assessed by self-report using the Timeline Follow-Back procedure at each visit to establish whether and when relapse has occurred and patch adherence. At the last visit, the PI or study staff will complete a brief exit interview with the participant to gain insight into their overall study experience and how the study may have changed their smoking behavior or thoughts about smoking. Participants will be debriefed and referred to area resources if additional cessation treatment is desired.

6 Month Follow-up Phone Call: Participants will be contacted by phone 6 months after their quit day to complete a brief interview about their current smoking status and nicotine dependence.

Selection of Subjects

In order to participate in this study, participants will be required to meet the following:

Inclusion criteria:

1. generally healthy (i.e. ambulatory, not currently sick)
2. interest in quitting smoking
3. between the ages of 18 and 65
4. smoking of at least 5 cig/day of a brand delivering ≥ 0.5 mg nicotine (FTC method) for > 1 year
5. an expired CO concentration of at least 10 ppm (to confirm inhalation) or urinary cotinine > 1000 ng/mL to confirm daily smoking (NicAlert=6)

Exclusion criteria:

1. inability to attend all required experimental sessions
2. desire to quit smoking prior to the study quit date
3. a quit attempt resulting in greater than 3 days of abstinence in the past 30 days
4. report of significant health problems including but not restricted to (e.g. chronic hypertension, emphysema, seizure disorder, history of significant heart problems, heart disease, heart attack in the past 90 days, irregular heartbeat)
5. unstable psychiatric conditions (any significant change in psychiatric symptoms during the past 3 months as determined by the study physician)

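### Relapse and 6-month smoking status rest on self-report from participants who can see their picture set, and nothing in the protocol keeps the interviewer unaware of assignment

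*Combined protocol and SAP*

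**What the plan says.** **Outcome.** Data Analysis & Statistical Considerations puts smoking cessation outcomes in the primary aim, alongside pre-quit dependence and smoking behavior, and expects MCE+ to do better. For the visits at weeks 1, 3, 6 and 10 after the quit day, Abstinence Period Visits gives the instrument: "Smoking behavior will be assessed by self-report using the Timeline Follow-Back procedure at each visit to establish whether and when relapse has occurred". The 6 Month Follow-up Phone Call paragraph adds: "Participants will be contacted by phone 6 months after their quit day to complete a brief interview about their current smoking status and nicotine dependence".

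**Objective measures.** Post-Quit Test Session gives the one explicit biochemical rule, for the visit after 24 hours without smoking: "Abstinence will be verified by expired breath CO level \leq 6 ppm". For the later visits the protocol says only: "Physiological measures will be collected and participants will complete questionnaires at each visit".

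**What participants see.** All participants photograph their smoking places before randomization ("Once participants have collected photographs of personal smoking environments they will return to the lab with the camera 1-2 weeks after the training session"). The MCE Sessions paragraph then separates the arms: "Participants will view picture stimuli depicting smoking environments including their personal smoking environments (MCE+ condition) or nature environments (MCE- condition".

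**What participants are told.** Screening Session states: "During the screening session all aspects of the study will be described to subjects and informed consent will be obtained".

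**Masking.** No section mentions masking of participants, session staff, interviewers or analysts. Data & Safety Monitoring opens study information to research staff as a group, with no exception for an outcome assessor.

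**The concern.** Timeline Follow-Back is a retrospective account. When it is taken by interview, the answer can depend on what the participant expects of the treatment and on how the interviewer probes. The participant cannot be masked here, because the pictures are the treatment. A control participant who has spent one to two weeks photographing smoking places can also see that those photographs go unused. The interviewer is therefore the main place where a safeguard could be put, and the protocol puts none there.

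The last visit adds a question of order. It holds the week-10 Timeline Follow-Back, an exit interview on how the study may have affected smoking, and a debriefing, with no sequence stated. The 6-month call comes after that debriefing.

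If false reports of abstinence were more common in one arm than the other, the excess would pass straight into the cessation difference. A positive result could then be put down to reporting, and the trial would hold no expectancy data with which to answer.

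**Working it through.** **No stated figure to reproduce.** The documents give no test, significance level, power, effect size or expected cessation rate. What follows is an illustration under assumptions.

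**Inputs from the documents**
- 80 eligible participants, 40 per arm; 68 expected to give useable data (Design & Procedures). With equal loss, 68/2 = 34 per arm.

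**Assumptions**
- Pooled two-proportion z test, two-sided 5%.
- True abstinence *q* is the same in both arms: 10%, 20% or 30%.
- In one arm, a share *d* of those still smoking report abstinence, over and above any false reporting in the other arm. The documents give no basis for a value of *d*.

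**Step 1, apparent difference.** Reported abstinence in the affected arm is q + d(1 − q), so the spurious difference is d(1 − q).
- q = 0.30, d = 0.05: 0.05 × 0.70 = 0.035, or 3.5 points
- q = 0.30, d = 0.10: 0.10 × 0.70 = 0.070, or 7 points

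**Step 2, hand check.** SE = sqrt(2 × 0.3 × 0.7/34) = 0.111. The shifts are 0.035/0.111 = 0.32 SE and 0.070/0.111 = 0.63 SE. P(|Z + 0.32| > 1.96) is about 0.06, and P(|Z + 0.63| > 1.96) is about 0.10.

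**Step 3, exact binomial enumeration, 34 per arm, no true effect.** Chance of a significant result:

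| True abstinence | d = 0 | d = 5% | d = 10% | d = 20% |
|---|---|---|---|---|
| 10% | 5.7% | 9.4% | 18.9% | 49.1% |
| 20% | 5.3% | 7.2% | 12.7% | 32.6% |
| 30% | 5.4% | 6.6% | 10.1% | 23.5% |

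With 40 per arm and 30% abstinence, the rates at d = 5% and 10% are 6.1% and 9.8%. The test is symmetric, so the same rates apply whichever arm over-reports; only the favoured arm changes.

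**Step 4, scale.** At 34 per arm and a 30% control rate, the true difference detectable with 80% power is about 33.5 points. A 3.5 to 7 point distortion is small beside that, but it is enough to raise the error rate.

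**Limit of the calculation.** Only false reports of abstinence are counted. A relapse given the wrong date is still a relapse: it would affect an analysis of time to relapse but not the proportion relapsed.

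**The case against.** The strongest reply is that the protocol is silent rather than wrong, and that several features limit the risk.

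- **Matched control.** Both arms have the same sessions, cigarettes, patches and imagery instruction. Everyone views some MCE- images before randomization. Knowing one's picture set is not knowing which set is expected to work. This stands, and it limits expectation differences without removing them.
- **Objective measures.** The 24-hour result has a CO criterion, so the point does not reach it. MCE Sessions lists CO among what it then calls physiological measures, so CO may well be taken at the abstinence visits too. This also stands, but no rule lets it confirm or overturn a reported relapse status.
- **Payment.** Abstinence-period visits are paid per visit, so the stated payments do not reward a false report there. This stands.

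A reader might infer two further things that the text does not support. One is that the staff who run the picture task also take the relapse interview. The protocol names no one for the Timeline Follow-Back, so overlap is possible but not stated. The other is that participants are told which picture set should work. The screening sentence promises a full description of the study but does not say that the hypothesis is disclosed. The slides and consent form are not available to check, and the content of the final debriefing is not given. A request to reword those materials would presume what they say.

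**Conclusion.** The point holds as a gap in safeguards. Ten-week relapse and 6-month status rest on self-report from participants who can see their picture set. Nothing keeps the interviewer unaware of assignment, and no stated rule checks the report after the 24-hour session.

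The size and direction of any bias cannot be obtained from the documents. Under the assumptions shown (34 per arm, 30% true abstinence, 5–10% excess false reports in one arm), a nominal 5% test would reject about 6–10% of the time. The rate is higher if true abstinence is lower.

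It would be tempting to read this as a demonstrated bias towards MCE+, or as the trial's actual error rate. Neither follows. The stated hypothesis favours MCE+, but that does not show which way reports would lean, and the excess rate is assumed. Nor is this the trial's single primary comparison: cessation is one of several outcomes in the primary aim, and no one endpoint is named. The change is worth making as a cheap improvement.

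**What to change.** In Abstinence Period Visits and 6 Month Follow-up Phone Call, adopt one of two arrangements:

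1. The participant completes the Timeline Follow-Back calendar before meeting staff and, at week 10, before the exit interview and debriefing; or
2. The Timeline Follow-Back and the 6-month interview are taken by an existing staff member who did not run that participant's MCE sessions and cannot see the assignment.

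The first does not cover the 6-month call, which is an interview by nature; the second arrangement is the one that serves there.

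In MCE Sessions, add one expected-benefit rating after session 1 and report it by arm.

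The cost is some scheduling and one added item, with no extra visits. The protocol gives no staff numbers, so the sponsor must judge whether the second arrangement can be staffed.

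These steps reduce interviewer influence and measure expectancy. They do not remove the participant's own reporting bias, and the trial report should say so.

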Potential participants will be recruited via community advertisements and websites at Duke University Medical Center. Participants will be recruited through flyers, direct mailings, television, radio, newspaper, bus, and on the internet (Craigslist advertisements, trianglesmokingstudies.com, ResearchMatch). Potential subjects can complete an on-line Qualtrics screening survey accessed from our website, after which they will be called to either be told they were not eligible or to complete a phone screen. During a phone screening interview, the study will be described in detail and participants will be asked questions over the phone to determine initial eligibility. If eligible and interested, they will be scheduled for an informed consent and screening visit.

Participants will receive no payment for the phone screening. Participants will receive \$10 in cash for completing the screening session, regardless of eligibility as long as they pass the breath alcohol test, drug test criteria, and meet the minimum requirements for breath carbon monoxide levels (or urinary cotinine levels). Individuals who do not pass these tests will be dismissed from the screening session without payment. Participants will receive \$25 each for the picture taking training and camera return sessions, \$30 for each MCE Session, \$25 for the post-quit test session, \$50 for meeting criteria for 24 hour abstinence, and \$30 for each abstinence period visit. The total amount earned for completing all sessions of the study is \$435. The only payments received in cash are the payments dispensed at the screening session (\$10) and post-quit test session (\$25 for session, \$50 for meeting abstinence criteria). All other payment will be received by check after completion of the study. Participants will receive \$10 for completing the 6 month follow-up phone call. Total compensation for attending sessions and completing all phone calls is up to \$445.

Consent Process

The PI, Research Coordinator, or Research Assistant will obtain consent from each participant. The person obtaining consent provides the participants with a written document explaining the procedures and risks, and reviews the PowerPoint presentation and answers any questions. A signed copy of the informed consent form will be given to each participant. Participants are informed that they may withdraw from participation in the study at any time without penalty.

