Data Analysis & Statistical Considerations

The primary aim of this study will evaluate the effects of MCE+ (vs. MCE-) on pre-quit nicotine dependence and smoking behavior, and smoking cessation outcomes. The premise is that the EXT/MCE+ will result in greater decreases in pre-quit nicotine dependence and smoking behavior and better cessation outcomes as compared to the EXT/MCE- group. Secondarily, we will examine reactivity (craving, physiology) in response to a set of standard smoking cues following abstinence and hypothesize less reactivity in the MCE+ group.

With the second aim of the study we will investigate whether among participants in the EXT/MCE+ group, EXT engagement (compliance with smoking VLNCs), EXT response (decrease in smoking behavior), MCE response (decreased craving across MCE sessions), and post-quit cue-reactivity predict smoking cessation outcomes. The proposition is greater compliance with, and response to smoking

VLNCs and greater decreases in craving across the course of MCE and in the cue-reactivity assessment will be associated with better smoking cessation outcomes.

Data & Safety Monitoring

Data capture will occur in several ways. All source documents will be stored in the participant binders. Research materials include questionnaires, expired air samples for analyzing carbon monoxide and breath alcohol levels, and urine samples for drug and pregnancy screens. Research data without identifiers will be maintained in a locked room and on password-protected computers in the research staff workplace, with only numeric codes identifying subjects. Study consent forms and any PHI will be stored in a locked file cabinet in a separate location from the study data. The link between the participants' names and codes will be stored on a password protected spreadsheet on a secure server. All information collected as part of this study will be accessible only to research staff. The Subject Identifier will be a numeric code that will include information about study number and subject ID number.

It will be made clear to participants that all information obtained during assessments is confidential and that no information will be shared with the participants' clinicians unless the participant requests this in writing. All investigators and staff associated with this project have been trained, and new hires will be trained, on human research ethics in accordance with the requirements of the local institutions.

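### The cotinine route in inclusion criterion 5 has no CO floor, so an entrant whose CO is 6 ppm or less while smoking can pass the 24-hour abstinence check without abstaining

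*Combined protocol and SAP*

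**What the plan says.** **Entry.** Under Selection of Subjects, inclusion criterion 5 requires "an expired CO concentration of at least 10 ppm (to confirm inhalation) or urinary cotinine > 1000 ng/mL to confirm daily smoking". The two markers are alternatives, and the section on recruitment and compensation repeats them as such. No CO minimum is attached to the cotinine route. Criterion 4 sets the smoking floor low: "smoking of at least 5 cig/day of a brand delivering" at least 0.5 mg nicotine.

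**Check.** Under Post-Quit Test Session: "Abstinence will be verified by expired breath CO level" at or below 6 ppm. No second marker is named, no comparison with the participant's own earlier CO is made, and cotinine-route entrants have no separate rule.

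**Consequence of failing.** In that case "s/he will only receive compensation for completing the visit, not for maintaining abstinence". The compensation section sets $50 "for meeting criteria for 24 hour abstinence". No exclusion from the session or from any analysis is stated.

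**Patch.** After the three-week treatment period "participants will quit smoking while continuing to wear the nicotine patch".

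**Use of the session.** The Data Analysis section states, as a secondary part of the first aim, that "we will examine reactivity (craving, physiology) in response to a set of standard smoking cues following abstinence". The second aim uses post-quit cue-reactivity as one of four predictors of cessation within the MCE+ group.

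**The concern.** The cotinine route only matters for people whose CO is below 10 ppm, since everyone else qualifies on CO. The plan thus makes room for low-CO daily smokers, and then judges their abstinence by an absolute CO cut that some of them may already meet while smoking. For those people a passing result carries no information about whether they stopped.

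The cue-reactivity measure is meant to be taken after abstinence. Craving and physiology recorded in someone who smoked that morning are a different measurement, and mixing the two would blur both the comparison of arms and the prediction analysis in the MCE+ group. The cash payment also rewards a claim of abstinence that the check could not contradict for these entrants.

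**Working it through.** The plan states no figure that this point could reproduce. The check is a comparison of two rules, followed by an illustration of scale.

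**Step 1: set the rules side by side.** Inputs: eligible if CO ≥ 10 ppm or urinary cotinine > 1000 ng/mL (criterion 5); verified abstinent if CO ≤ 6 ppm (Post-Quit Test Session). Take a smoker with cotinine above 1000 ng/mL and ask whether the usual smoking CO already satisfies the abstinence cut.

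| CO while smoking (ppm) | Route that admits | Meets the ≤ 6 ppm cut at that level |
|---|---|---|
| 0-6 | cotinine only | yes |
| 7-9 | cotinine only | no |
| 10 or more | CO | no |

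The overlap is confined to the first row. Those at 7-9 ppm also enter by cotinine alone, but fail the cut unless their CO falls.

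**Step 2: can the other entry marker fill the gap?** No. The patch supplies nicotine after quit day, so cotinine would be present whether or not the participant smoked.

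**Step 3: scale.** Let q be the share of entrants whose CO is 6 ppm or less while smoking. The documents do not give q. I assume 2% to 5%, with N = 80 planned participants (Design & Procedures).

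- Expected number = N × q: 80 × 0.02 = 1.6; 80 × 0.05 = 4.0.
- Chance of at least one = 1 − (1 − q)^N: 1 − 0.98^80 = 0.80; 1 − 0.95^80 = 0.98.
- In the MCE+ group alone (40 planned), which the second aim uses: 40 × 0.02 = 0.8; 40 × 0.05 = 2.0.

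**Step 4: effect on the verified group.** Let a be the share truly abstinent at 24 hours (assumed, and the same in low-CO entrants). Suppose every abstinent participant passes, every non-abstinent low-CO entrant passes, and no other non-abstinent participant does. The falsely verified share of those who pass is (1 − a)q / [(1 − a)q + a].

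| a | q = 2% | q = 5% |
|---|---|---|
| 0.3 | 0.014 / 0.314 = 4.5% | 0.035 / 0.335 = 10.4% |
| 0.5 | 0.010 / 0.510 = 2.0% | 0.025 / 0.525 = 4.8% |
| 0.7 | 0.006 / 0.706 = 0.8% | 0.015 / 0.715 = 2.1% |

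These figures show orders of magnitude only; neither q nor a comes from the documents.

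**The case against.** The strongest reply is that the affected group may be close to empty. The documents give no count of cotinine-route entrants, and those at or below 6 ppm are only a subset of them. Screening CO is also not shown to be a typical smoking value, because no time since the last cigarette is set at screening. The first standardised reading is at the training session, after a usual-brand cigarette. Participants then smoke VLNC cigarettes, and the risk section warns that CO may rise. All of this stands. It limits the size of the problem but does not remove the overlap between the two rules.

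A second reply is that little depends on the check. That is largely right: failing it costs the $50, and the Data Analysis section defines no analysis set by it.

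Three stronger readings are tempting, and the documents support none of them.

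- *A reader might infer that the cessation outcome is compromised.* Whether and when relapse occurs is established by Timeline Follow-Back self-report at the abstinence-period visits. The 24-hour check is not stated to define cessation, so any effect there is indirect.
- *A reader might infer bias between arms, or a problem concentrated in the lower patch-dose group.* Eligibility is settled before randomisation and is the same for both arms. Nothing in the documents links low CO to a patch-dose group, and patch dose is not a planned comparison.
- *A reader might infer that the check fails for everyone.* CO does clear within hours: at an assumed half-life of 4-6 h, a fall from 10 to 6 ppm takes log2(10/6) = 0.74 half-lives, about 3 to 4.5 h. That is a general limit of CO over a 24-hour window. It applies equally to people who entered on CO and is not caused by criterion 5.

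**Conclusion.** The point holds in limited form. As written, the plan admits a smoker on cotinine at any CO level, and it verifies 24-hour abstinence by a CO value that such a smoker may already show. For an entrant at or below 6 ppm while smoking, the verification is uninformative, and no substitute marker is available while the patch is worn.

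The size is unknown and probably modest: about 2-4 of 80 under the assumed 2-5%. It would be wrong to count every cotinine-route entrant, since those at 7-9 ppm do not meet the cut at their usual level. The consequence is confined to the $50 payment and to the premise that cue-reactivity was measured after abstinence (a secondary outcome in the first aim, a predictor in the second). The expected effect is misclassification that blurs those results rather than an imbalance created by the entry rule. The conclusion about the rules rests on the text alone; only the scale rests on assumptions.

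**What to change.** **If criterion 5 can still be amended:** for the cotinine route, require expired CO above 6 ppm as well as urinary cotinine > 1000 ng/mL. This removes the overlap at entry.

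**If enrolment is under way or complete:** flag each participant whose pre-randomisation CO, at the screening or the training session, was 6 ppm or less. Treat that person's 24-hour abstinence as self-reported only. Keep them in the main analysis, and repeat the post-quit cue-reactivity analyses for both aims without them as a sensitivity analysis. Report the number flagged.

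**What to avoid:** CO from the MCE sessions should not be used to define abstinence or exclusions, for example by requiring a set percentage fall from it. Those readings come after randomisation, and the plan hypothesises that MCE+ reduces pre-quit smoking. If that is true, such a rule could relabel or remove more of the MCE+ participants who responded, and so introduce a selection difference that the entry rule itself does not cause.

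**Cost:** one amended criterion or one flag and one sensitivity analysis. No new measurement is needed, because CO is already taken at both pre-randomisation sessions. The amended criterion would lose a few low-CO light smokers at screening. It does not change the fact that CO is a short-window marker for every participant.
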